Thus, good evidence suggests that at least acute treatment with ARBs could ameliorate lung injury in COVID-19. We therefore propose to test losartan in a Phase I proof of concept and safety trial. The primary hypothesis to be tested is that losartan treatment is safe in the setting of acute SARS-CoV-2 infection. Secondarily, losartan can potentially reduce the length of respiratory failure due to SARS-CoV-2.

Significance

Importance of the problem: As outlined above, there is currently no data that supports specific treatment options for respiratory failure in COVID-19. There are active or soon to be active clinical trials that may show promise in this space such as blocking IL-6 with tocilizumab²⁰ or using hydroxychloroquine. None of these therapies are without side effects and alternative or additional approaches could lessen the burden of respiratory failure in this patient population.

Approach and Protocol

This is an open label, phase 1 clinical trial to evaluate the safety of losartan in respiratory failure due to COVID-19.

Clinical Trial setup:

Detailed inclusion and exclusion criteria are listed below. Briefly, 50 patients with COVID-19 and respiratory failure who meet criteria and agree to participation in the study will be placed on losartan 25 mg daily on study day 0. If parameters are met the dose of losartan will be increased to 50 mg on study day 3. Participants will continue losartan until they experience resolution of respiratory failure (normal oxygen levels on room air), are discharged from the hospital, meet stoppage criteria (detailed below) or complete 14 days of therapy.

Primary hypothesis and endpoint:

- Losartan is safe in acute respiratory failure due to SARS-CoV-2.

Secondary endpoints:

- Losartan reduces the number of days on supplemental oxygen in respiratory failure due to COVID-19
- Incidence of mechanical ventilation use
- Days on mechanical ventilation
- Incidence of non-invasive positive pressure ventilation or heated high flow nasal cannula use
- Days on non-invasive positive pressure ventilation or high flow nasal cannula
- Incidence of transfer to ICU from non-ICU hospital bed
- ICU length of stay (days)
- In-hospital mortality
- Hospital length of stay (days)
- Cumulative incidence of severe adverse events
- Cumulative incidence of adverse events
- Change from baseline in oxygenation

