Since there is no information on the effects of losartan in human beings suffering from COVID-19, a statistical analysis based on efficacy is not possible. From a safety perspective, we would accept considering losartan equivalent or superior to the comparison group not receiving losartan (historical or no consent) if there is a $\pm 20\%$ difference in total AE/SAEs. Historical controls will be matched with study participants based on upon age, sex and disease severity in a 2:1 ratio for safety comparison. From a safety perspective, losartan's long track record as a safe medication is reassuring. See section on DSMB for further details on safety monitoring and analysis.

Confidentiality

All information provided by the subject to the investigators, and all information that is collected about the subjects by the investigators, shall be kept confidential to the extent that is provided by law. Computer data files will be stored and backup up to secure, HIPPA compliant, password protected computers and servers. Electronic data capture into REDCap system will be used. Access to these databases will be restricted to individuals associated with the study who require access to the data to perform their duties. These individuals will be named by the principal investigator prior to initiation of the clinical trial. The subject's actual identity cannot be ascertained exclusively from these data and the subject's name shall not be used in any publications. All investigators and staff involved in the research protocol will be bound by this agreement of confidentiality.

Adverse Event and Serious Adverse Event Documentation

Definition of an Adverse Event

For the purpose of this protocol, an AE will be defined as any untoward medical occurrence in a subject during the study listed under DMSB - Anticipated Adverse Events and Grading Scale section of this protocol as well as safety monitoring data listed on table 1 as well as stoppage criteria for losartan.

The event does not necessarily have a causal relationship with the treatment. AEs will be collected for both study groups, treatment and control from the time the ICF is signed until the subject completes study participation.

Definition of a Serious Adverse Event

An SAE is any AE that meets any of the following outcomes:

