 - Any serious AE or SAE attributable to study drug will be shared with the medical monitor and safety and monitoring group within 24 hrs. The members will make the decision whether or not to stop the trial.
- All SAEs will be reported to the safety and monitoring group and the appropriate agencies including FDA and IRB as required.
- All adverse effects will be reported according to the rules to the FDA, the IRB and our internal DMSB
- Initial interim analysis on safety will be done after the first 5 patients and reviewed by the internal DSMB.
- The DSMB may stop the study due to safety or futility.
- All DSMB reports will be shared with the IRB.

Safety Reporting

Data monitoring plans will be implemented as follows: The study will be closely monitored by the PI and Co-PIs. Any relevant AE or SAE will be reported to the medical monitor and to the DSMB (separate charter).

- DSMB meeting will occur after the first 5 patients, 25 patients and at end of study, or more frequently if needed.
 - Safety monitoring will be done by the DSMB. Safety monitoring will be done as follows: The investigators will continuously monitor the study for side effects. If any AE or serious adverse events (SAEs) occur, the physicians will assess the event and report them to the appropriate authorities if needed as per Good Clinical Practice. Subjects might be withdrawn from the study if they experience intolerance to the study medication, initially based on the investigators' discretion.
 - All adverse effects will be discussed among the investigators
 - If deemed severe the data will be shared with the medical monitor and the safety and monitoring group. The group will make the decision whether or not to stop the trial based on safety data.
- All SAEs will be reported to the IRB and the appropriate agencies including FDA as required.

- All adverse effects will be reported according to the rules to the FDA (if needed), the IRB and the DSMB.

Safety Reviews

Safety review will occur at least every month and/or if a SAE occurs. The internal safety and monitoring group will meet after the first 5 patients, 25 patients and at end of study or more frequently if needed. If needed, the biostatics core will assist in data analysis for adverse events as well (fee for service basis). However, this is a small study.

Removal of Subjects from Study

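### The only numerical criterion for the primary safety conclusion, a ±20% difference in total AE/SAEs, has no confidence limit, scale or counting unit, so it can declare equivalence when the data cannot exclude an excess well beyond that margin

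*Combined protocol and SAP*

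**What the plan says.** The section Primary hypothesis and endpoint gives one statement, "Losartan is safe in acute respiratory failure due to SARS-CoV-2", with no measure or test. Clinical Trial setup gives the size: "Briefly, 50 patients with COVID-19 and respiratory failure who meet criteria and agree to participation". Sample size and Statistics gives the criterion: "we would accept considering losartan equivalent or superior to the comparison group not receiving losartan (historical or no consent) if there is a". The margin there is ±20%, and the text goes on to say what it applies to and how historical controls are chosen: "difference in total AE/SAEs. Historical controls will be matched with study participants based on upon age, sex and disease severity in a 2:1 ratio". The criterion names both historical and no-consent controls, but matching is described only for the historical ones.

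The same section then points elsewhere: "See section on DSMB for further details on safety monitoring and analysis". The DSMB material gives meeting times, reporting routes and a right to stop, for example "Initial interim analysis on safety will be done after the first 5 patients and reviewed by the internal DSMB". Under Safety Reviews it adds "If needed, the biostatics core will assist in data analysis for adverse events as well (fee for service basis". It gives no method for comparing the groups. A separate DSMB charter is mentioned but is not among the supplied documents.

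The Secondary endpoints include "Cumulative incidence of adverse events", but nothing ties that quantity to the ±20% rule.

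**The concern.** A margin can be applied to a point estimate or to a confidence limit. The text mentions no limit, so as written it applies to the observed difference. With 50 against 100 patients, an observed difference just inside the margin is compatible with a true difference far outside it.

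The margin also has no scale (percentage points or relative) and no counting unit (patients with an event, or events per patient). If these are settled after the data are seen, in an open-label study, the choice can settle the conclusion. At stake is the trial's main statement, that losartan is equivalent or superior to no losartan on safety.

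**Working it through.** **Inputs.** From the protocol: 50 losartan patients, 2:1 matching (hence 100 controls if the ratio is reached), margin 20%. Assumed: control rates of 20-60% of patients with an event, and independent groups. The protocol states no alpha, power or AE rate, so the 50 has no derivation to reproduce.

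**1. A dataset that passes, points reading.** Take 30/50 (60%) against 40/100 (40%).
- Difference = 0.20, which meets the margin.
- SE = √(0.6×0.4/50 + 0.4×0.6/100) = √(0.0048 + 0.0024) = 0.0849.
- Wald 95% CI: 0.20 ± 1.96×0.0849 = 0.034 to 0.366. Newcombe 95% CI: 0.031 to 0.354.
- If exactly 20 points must fail, 29/50 against 40/100 (18 points) still passes, with a Newcombe upper limit of 0.335.

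The data leave open an excess of about 35 points under a rule meant to allow 20.

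**2. How often the rule accepts.** Exact enumeration, for control rate p and true excess δ:

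P(accept) = Σ Σ Bin(x₁; 50, p+δ) × Bin(x₀; 100, p), summed over all x₁, x₀ with x₁/50 − x₀/100 ≤ 0.20.

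For the ratio reading the condition is (x₁/50)/(x₀/100) ≤ 1.2.

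| Control rate | True +20 points, points rule | True +20 points, ratio rule |
|---|---|---|
| 20% | 53% | 3% |
| 30% | 52% | 6% |
| 40% | 52% | 10% |
| 50% | 52% | 13% |
| 60% | 52% | 17% |

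If exactly 20 points fails, the points column becomes 47-48%. On points, a true +25 is accepted 26-30% of the time and a true +30 is accepted 7-13%. The dataset in step 1 has a ratio of 0.60/0.40 = 1.5, so it passes on points and fails on the ratio.

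**3. Events per patient, relative reading.** At one event per control patient, 60 events in 50 patients against 100 in 100 gives a rate ratio of 0.60×2 = 1.20, which passes. With Poisson counts the SE of the log ratio is √(1/60 + 1/100) = 0.163, and the upper 95% limit is 1.2×exp(1.96×0.163) = 1.65. At five events per control patient (300 against 500) the upper limit is 1.38. The limit exceeds the margin on this reading too.

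**4. The lower side.** Read literally, a ± band fails a drug that lowers AEs by more than the margin. A fall from 60% to 30% is a difference of −30 points, outside ±20, although the same sentence also allows losartan to be called superior.

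**5. The ceiling.** Definition of an Adverse Event counts the Table 1 abnormalities whatever their cause, and Grade 1 in Table 1 includes small laboratory deviations. If patients with any AE are counted and the observed control rate is 80%, the largest possible excess is 100 − 80 = 20 points. Above 80%, a 20-point margin cannot be exceeded.

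**6. An upper-limit rule instead, points scale.** Accept if difference + z×SE < 0.20, by the same enumeration.

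| Control rate | No true difference, z = 1.645 | No true difference, z = 1.96 | True +20 points, z = 1.645 |
|---|---|---|---|
| 20% | 87% | 81% | 6% |
| 30% | 81% | 71% | 5% |
| 40% | 76% | 66% | 5% |
| 50% | 74% | 66% | 5% |
| 60% | 77% | 66% | 4% |

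The point-estimate rule accepts over 99% when there is no true difference.

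**The case against.** The strongest reply is that this is an open-label, non-randomised phase 1 study with tentative wording, where defining the metric and reporting an interval might suffice. That stands as a reason to limit the severity. It does not explain a declaration of equivalence on an undefined measure. The protocol says only that an efficacy-based calculation is not possible; the safety rule is its own.

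The points reading fits the word total less well than a relative difference in events. On the events reading gross harm is usually caught: in simulations assuming 1-5 events per control patient, a true ratio of 1.5 was accepted in 0-18% of trials and 2.0 in under 2%. This stands, and the 52-53% belongs to the points reading only. Acceptance near one half at the margin is also what any point-estimate rule gives. The 20-60% rates may be too low if every Grade 1 laboratory change counts.

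Three stronger readings are tempting, and the documents do not support them.
- **That the defect is passing data whose 95% CI excludes zero.** Any non-inferiority margin allows this. With 49/50 against 86/100 the difference is 0.12 and the SE is 0.040, so 0.12 + 1.645×0.040 = 0.186 passes the upper-limit rule in step 6, yet the Newcombe lower limit is +0.019.
- **That raw totals would be compared, so a doubled per-patient rate could pass.** The protocol states the 2:1 ratio in two sections, so an unscaled comparison is improbable.
- **That participants are left unprotected.** Patient-level stoppage criteria and DSMB reviews operate during the trial. The gap concerns the final conclusion.

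**Conclusion.** The point holds and should be fixed. In the supplied documents, the only numerical criterion for the primary hypothesis lacks a confidence limit, a scale and a counting unit; the unseen charter might add detail. The textual gaps need no assumption. The operating figures assume 50 against 100 independent patients, one yes/no outcome each and the stated control rates; matching or a shortfall of controls would move them somewhat. The most secure statement is that a passing result can leave an upper 95% limit well past the sponsor's own margin: about 35 points against 20, or a rate ratio of 1.38-1.65 against 1.2. Severity stays below the highest level because the study is small and uncontrolled by randomisation, and no interval covers bias from the choice of controls.

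**What to change.** Before the data are analysed:

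1. State a per-patient metric that is not near its ceiling, for example events per patient-day or patients with a Grade 3 or higher AE/SAE, and state the scale. Confirm that 20% is still the intended margin for that metric.
2. State whether matched historical controls, no-consent controls or both enter the comparison.
3. Conclude non-inferior safety only if the upper limit of a pre-stated one-sided confidence interval, from a method that respects the 1:2 matching, is below the 20% margin. Set no lower limit.
4. If a relative 20% is meant, or the limit is not met, report the estimate with its interval and make no equivalence claim.

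No extra patients or procedures are needed, but the conclusion becomes harder to reach. On the points scale with independent samples, acceptance of a drug with no AE effect falls from about 99% to 74-87% with a one-sided 95% limit, or to 66-81% with the upper limit of a two-sided 95% interval. In return, acceptance of a true +20 points falls to 4-6% with the one-sided 95% limit. On the patient-ratio scale the one-sided rule would accept a no-effect drug in only 11-35% of trials. Reaching 80% there would take n = (1.645 + 0.8416)² × 1.5 × [(1−p)/p] / (ln 1.2)² losartan patients, about 186 at p = 60% and 1,116 at p = 20%, each with two controls. That is why item 4 asks for estimation only on a relative scale.

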Patients that request to not be treated with Losartan will be approached by the study team to request permission for their standard of care treatment and data be followed and recorded by the research team for this study. Patients that agree, will sign the consent form, but will not provide a blood sample for research. We will also collect medical information relating to safety criteria on historical controls treated at the University of Kansas Hospital in the 30 days prior to the study start date (3/25/2020) and during the study period. These controls will be retrospectively identified through query of the electronic health record. We will attempt to include controls that meet all criteria for enrollment into the study but to achieve a ratio of controls to study participants of 2:1 may need include some with exclusion criteria (excluding prior ACE inhibitor or ARB use). Controls identified retrospectively will not undergo informed consent as this represents minimal risk.

Losartan

Losartan is an FDA-approved ARB widely prescribed for treatment of hypertension, heart failure, and for renal protection in patients with diabetes. The doses proposed in this study are well tolerated by non-hypertensive patients without significant effect on blood pressure. The proposed starting dose of losartan is 25 mg orally per day with increase to 50 mg orally per day on day 3 if tolerated until they patient is discharged from the hospital, met stoppage criteria (above) or completed 14 days of therapy.

The most common side effects are fatigue and dizziness. Serious adverse events that are rare include angioedema, hypotension, renal dysfunction or failure, blood dyscrasias, hepatitis, or rhabdomyolysis. The following are meant to mitigate risk to the subjects: Dosing will be done in an inpatient setting with clinically indicated close observations of blood pressure and organ dysfunction (blood work). Subjects with hyperkalemia, renal dysfunction, or who are taking potassium supplements will not be enrolled into the study. Participants will be given written descriptions of potential side effects and potential responses to the side effects.

Sample size and Statistics

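### The ±20% safety rule compares total AE/SAEs with no denominator and no common observation window, so unequal observed time can move the result with no change in the AE rate

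*Combined protocol and SAP*

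**What the plan says.** Sample size and Statistics would consider losartan "equivalent or superior to the comparison group not receiving losartan (historical or no consent") "if there is a $\pm 20\%$ difference in total AE/SAEs". It does not say whether 20% is relative or absolute, whether the total is per patient or per day, or whether a point estimate or an interval decides.

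Definition of an Adverse Event collects AEs in both groups "from the time the ICF is signed until the subject completes study participation". The visible text gives no day count for that end point. The Control section draws further controls retrospectively from the health record without consent, so the stated starting event cannot apply to them.

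Clinical Trial setup plans "Briefly, 50 patients with COVID-19 and respiratory failure". The Control section may relax the exclusion criteria "to achieve a ratio of controls to study participants of 2:1", which means about 100 controls. Matching is "based on upon age, sex and disease severity in a 2:1 ratio for safety comparison"; time observed is not a factor.

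Losartan itself is given until respiratory failure resolves or patients "are discharged from the hospital, meet stoppage criteria (detailed below) or complete 14 days of therapy". Cumulative incidence of AEs and of severe AEs is listed under Secondary endpoints, with no time horizon.

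**The concern.** A total depends on how often events occur and on how long someone is looking. The AE definition points to Table 1, the anticipated losartan side effects and the stoppage criteria. Most of these are laboratory values, blood pressure or vasopressor use. Such findings are likely, by inference, to be recorded mainly in hospital, and the visible text schedules no visit after discharge. Stay and survival differ between patients and may differ between groups, so observed time may differ too.

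The safety verdict could then go wrong in two ways. A higher daily AE rate on losartan could pass because fewer days were observed, or a drug with no effect on the rate could fail because more days were observed. For retrospective controls the length counted would depend on when the analyst starts the clock, which the plan leaves open.

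**Working it through.** **What can be reproduced.** The plan gives no alpha, power or expected AE rate, so no stated calculation lies behind the ±20% or the 50 patients.

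**Inputs from the plan:** 50 treated patients, about 2 × 50 = 100 controls, a margin of 20%. **Assumed:** a constant daily AE rate; 20% read as relative and per patient; the ratio *f* of mean observed days, losartan to control.

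**Why a per-patient reading is needed.** If the total were a raw count, equal rates and equal time would give 50/100 = 0.50 from the group sizes alone. Some per-patient scaling must be intended, but it is not written.

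**Formula.** Per-patient total = daily rate × mean observed days. So total ratio = daily rate ratio × *f*. Because superiority is also accepted, only the upper limit of 1.20 counts against losartan. The largest daily rate ratio accepted is therefore 1.20/*f*.

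| *f* | Total ratio at equal daily rates | Largest daily rate ratio accepted (1.20/*f*) | Daily rate ratio at equal totals (1/*f*) |
|---|---|---|---|
| 1.25 | 1.25 (outside the band) | 0.96 | 0.80 |
| 1.0 | 1.00 | 1.20 | 1.00 |
| 0.9 | 0.90 | 1.33 | 1.11 |
| 0.8 | 0.80 | 1.50 | 1.25 |
| 0.7 | 0.70 | 1.71 | 1.43 |

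**Chance of acceptance.** Assume 10 control days, 0.15 AEs per day in controls, a true daily rate ratio of 1.5 and *f* = 0.8. Expected events are 50 × 8 × 0.225 = 90 on losartan and 100 × 10 × 0.15 = 150 in controls. The per-patient ratio is 1.80/1.50 = 1.20 and the per-day ratio is 0.225/0.15 = 1.50. In a Poisson simulation (200,000 runs), the point estimate was at or below 1.20 in about 51% of runs per patient and 5% per patient-day. With control rates from 0.05 to 0.30 per day, the per-patient figure stayed at 50–51%. The per-day figure was 18%, 5% and 1% at 0.05, 0.15 and 0.30.

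**Does cumulative incidence remove the problem?** With no fixed horizon, it does not. At the same hazard in both groups and 10 against 8 days:
- hazard 0.05/day: (1 − e^−0.4)/(1 − e^−0.5) = 0.330/0.393 = 0.84
- hazard 0.10/day: (1 − e^−0.8)/(1 − e^−1.0) = 0.551/0.632 = 0.87

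**The case against.** Four stronger readings are tempting, and the documents do not support them.

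- *Participation ends at recovery, discharge, stoppage or 14 days.* Those events end the drug. AE counting ends with participation, which is a separate event. The plan has criteria for resuming after a stop and asks withdrawn subjects to allow follow-up off drug.
- *AEs can be seen only in hospital.* This is an inference. The SAE definition also counts later deaths suspected to be delayed toxicity. The study schematic is not shown and the DSMB charter is a separate document, so a defined window cannot be ruled out.
- *A shorter stay is losartan's hypothesised effect, so the safety rule is confounded with efficacy.* The stated idea is "Secondarily, losartan can potentially reduce the length of respiratory failure due to SARS-CoV-2". Hospital length of stay is a secondary endpoint with no direction. A link is plausible but not stated.
- *A 20% shorter observed time uses up the margin.* At equal rates it moves the total to the favourable edge. On the harmful side the tolerance widens, from 1.20 to 1.50.

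The best argument on the other side concerns the remedy. A per-day rate can mislead too, because recovery and death change its denominator. Assume 0.20 AEs per day during respiratory failure and 0.02 per day in convalescence, the same in both groups, with 6 + 4 days for controls and 6 + 2 for losartan. Events per patient are 6 × 0.20 + 4 × 0.02 = 1.28 and 6 × 0.20 + 2 × 0.02 = 1.24, a ratio of 0.97. Per day they are 1.28/10 = 0.128 and 1.24/8 = 0.155, a ratio of 1.21. A per-day rule would fail a harmless drug that the total passes. Fewer AEs through faster recovery is also a real benefit, so a per-patient total is a legitimate measure. This stands, and it rules out the per-day rate as the sole criterion. It does not supply the missing denominator or window.

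**Conclusion.** The point holds in limited form. As written, the rule for the primary safety comparison has no denominator and no common window, retrospective controls have no starting point, and matching does not balance observed time. Unequal observation can therefore move the verdict in either direction.

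The size is conditional. The tabulated ratios rest on assumed time ratios, a constant daily rate and a relative, per-patient margin; the documents give no AE rates or lengths of stay. If events cluster early, if each event type counts once per patient, or if participation stops by Day 14, the effect is smaller. If 20% is an absolute difference, the tabulated limits do not apply. The text does not show that observed time will differ or in which direction. It shows that nothing in the rule protects against a difference.

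**What to change.** In Sample size and Statistics:

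1. Count AEs and SAEs in both groups over one window, from Day 0 to Day 14. For retrospective controls, set a matched index day from the day the eligibility criteria are first met. Where a control has an exclusion criterion, as the plan allows, use the inclusion criteria. Exclusion criterion 13 lets a participant's Day 0 fall up to 48 hours after meeting the inclusion criteria, so give each control the same lag as its matched participant.
2. State how death and discharge before Day 14 are handled, identically in both groups.
3. State the ±20% as a relative comparison of events per patient, with a confidence interval.
4. Report beside it the rate per observed day (Poisson or negative binomial, log observed days as offset, robust errors by matched set), the proportion with any SAE, and deaths, so that early death does not look like low exposure.
5. Call losartan equivalent only if the per-patient and per-day results agree, or explain the difference by observed time.

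The cost is some added wording, a little more analysis and one extra variable. For historical controls the plan promises only safety-related information, so observed days would have to be extracted from the health record.

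### The safety acceptance rule pools all AEs and SAEs into one total, so mild events can offset an excess of serious events or deaths within the rule

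*Combined protocol and SAP*

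**What the plan says.** The primary hypothesis and endpoint is one statement: "Losartan is safe in acute respiratory failure due to SARS-CoV-2". It names no event type, rate or threshold. The only decision rule attached to safety is in Sample size and Statistics: "we would accept considering losartan equivalent or superior to the comparison group not receiving losartan (historical or no consent") provided the "difference in total AE/SAEs" lies within plus or minus 20%. The treated group is "50 patients with COVID-19 and respiratory failure who meet criteria and agree to participation in the study" (Clinical Trial setup). Historical controls are "matched with study participants based on upon age, sex and disease severity in a 2:1 ratio for safety comparison", so about 100.

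Under Definition of an Adverse Event, AEs include the anticipated events, the Table 1 safety data and the losartan stoppage criteria. No grade is excluded, and Grade 1 covers asymptomatic findings needing no intervention. The next definition reads "An SAE is any AE that meets any of the following outcomes", and death heads that list.

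The secondary endpoints include "Cumulative incidence of severe adverse events", the corresponding incidence for all AEs, and in-hospital mortality. None has a margin or test, or any part in the acceptance rule. The first of these speaks of severity, which is a grade, where the later definition concerns seriousness, which is an outcome.

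**The concern.** The trial exists to make one claim, that losartan is safe, and that claim is to be judged on a quantity that does not register seriousness. Counted by patient, an SAE adds nothing, because that patient already has an AE. Counted by event, a death counts once, as does a potassium value just above the normal limit. The patients have respiratory failure, frequent blood draws and many graded laboratory items, so mild events could well dominate the total.

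At stake is a report that correctly applies its pre-specified rule and states that losartan is equivalent or superior, next to secondary results showing more SAEs or deaths. The rule's missing scale, counting unit and confidence limit are a separate gap. With those supplied, a pooled total would still let mild events offset serious ones.

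**Working it through.** **Inputs.** From the documents: 50 treated, 2:1 controls (100), a 20% margin. The margin and the sample size have no stated derivation, so there is no figure of the plan's own to reproduce. All event rates below are assumptions, shown with ranges.

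**1. Largest SAE excess that still passes.** Read the margin as relative and on events. Let SAEs be a share s of the control total. If SAEs rise k-fold and non-serious events do not change, the total rises by s(k − 1). The rule passes while s(k − 1) ≤ 0.20, that is k ≤ 1 + 0.20/s.

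The last two columns give the chance that a true doubling of SAEs still gives totals within ±20%. They come from simulation at an assumed 4 events per patient, 50 v 100, with the rule applied to the point estimate. The overdispersed column uses a gamma patient effect with shape 1.

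| SAE share of control events | Largest SAE ratio that passes | Doubling passes, Poisson | Doubling passes, overdispersed |
|---|---|---|---|
| 5% | 5.0 | 94% | 68% |
| 10% | 3.0 | 85% | 63% |
| 20% | 2.0 | 50% | 49% |
| 30% | 1.67 | 16% | 34% |
| 50% | 1.4 | under 1% | 13% |

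**2. Offsetting by mild events.** Take 100 controls with 400 events, 40 of them SAEs (4.0 per patient). At the same rates, 50 treated patients would have 180 non-serious events and 20 SAEs.
- SAEs tripled to 60: (180 + 60)/50 = 4.8 per patient, exactly +20%.
- SAEs tripled and non-serious events down 10%: (162 + 60)/50 = 4.44, or +11%.

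**3. Deaths.** If a proportion d of controls die and each control has t events, doubling deaths raises the total by d/t. At d = 10% and t = 4 this is 0.10/4 = 2.5%. Over d = 5% to 20% and t = 2 to 6 it runs from 0.05/6 = 0.8% to 0.20/2 = 10%.

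**4. One illustration.** Treated 205 events (4.1 per patient), controls 400 (4.0): 4.1/4.0 = 1.025, a difference of 2.5%. These totals can contain 12/50 (24%) and 10/100 (10%) deaths. The other events are then 193/50 = 3.86 and 390/100 = 3.90 per patient, almost equal. For the deaths, the Wilson limits are 14.3% to 37.4% and 5.5% to 17.4%. The Newcombe interval for the 14-point difference is
- lower: 14 − √[(24 − 14.3)² + (17.4 − 10)²] = 1.8 points;
- upper: 14 + √[(37.4 − 24)² + (10 − 5.5)²] = 28.1 points.

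Fisher's exact p is 0.029. The example is borderline: one death fewer (11/50) gives p = 0.078. The calculation ignores the matching.

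**5. The patient-level reading.** Any-AE proportions of 46/50 (92%) and 90/100 (90%) differ by 2 points and are compatible with the same deaths. If 20% means percentage points, the largest possible excess is 100% minus the control proportion. The rule therefore cannot fail for harm once 80% or more of controls have an AE.

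**The case against.** The strongest reply is that nothing is concealed. AE incidence, severe-AE incidence and in-hospital mortality are each listed endpoints, so an excess would be reported. The statistics section also refers to the DSMB section. Under that section all SAEs go to the safety group, reviews follow 5 patients, 25 patients and the end of study, and the DSMB may stop the trial. This stands. A reader might infer that the pooled rule hides deaths from the report or from the DSMB; the documents do not support that. What the reply leaves open is the final claim. The DSMB section states no numerical limit for SAEs or deaths. A separate charter is mentioned but is not part of the document, and stopping a trial is a different decision from concluding safety.

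Second, the phrase could mean AEs and SAEs each within 20%. That is possible, though the text does not say so. Deaths would still have no criterion. They would be pooled with other SAE outcomes such as prolonged hospitalization.

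Third, the size of the problem depends on the SAE share. In respiratory failure the share may be large, and at 50% the rule stops an SAE ratio above 1.4 if other events are unchanged. That is fair, and it is why a range is given.

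Fourth, an SAE comparison at 50 v 100 is imprecise. This is true, but the precision of the pooled total comes largely from events that do not bear on serious harm.

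**Conclusion.** The concern holds in this form: the only acceptance rule for the safety claim has no criterion for SAEs or deaths, and under its natural reading mild events can offset an excess of either. The SAE ratio that still passes runs from 5.0 to 1.4 as the SAE share of control events runs from 5% to 50%. That range assumes a relative margin on events and unchanged non-serious rates.

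The death example might be taken to show that a clear excess would be accepted. It does not go that far: its rates are assumed and its significance turns on one death. It shows only that such data are compatible with passing.

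It is also unclear whether a death from progression of COVID-19 enters the total at all. AEs are limited to listed events and Grade 5 is a death related to an AE, while the SAE definition takes death from any cause. This is a further reason to count deaths directly. Because this is the only rule on the only primary claim, it should be corrected before the comparison is made.

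**What to change.** In Sample size and Statistics, replace the pooled total by three comparisons: (1) patients with at least one AE, (2) patients with at least one serious AE, (3) all-cause in-hospital deaths. Give each as a difference with its 95% confidence interval. Allow the claim of equivalence or superiority only if all three meet the rule on the upper confidence limit, with margins for SAEs and deaths that the sponsor states in advance. Otherwise report the estimates without the claim.

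Splitting the total is not enough on its own. In the illustration, +14 points of deaths lies inside a 20-point margin on the point estimate; only the upper limit of 28.1 exceeds it. Deaths need their own criterion because they can also be offset within the SAE count.

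Classify SAEs in retrospective controls from the chart, by the same definition and over the same time window as in treated patients. The present start of AE collection, at signing of consent, cannot apply to controls who are not consented. In Secondary endpoints, use serious in place of severe.

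The cost is more than wording. Control charts need extra review, since several SAE outcomes require judgment. The claim is also harder to meet. Even with identical observed rates, the Newcombe upper limit is 12.2 points for deaths of 5/50 v 10/100 and 16.0 points for SAEs of 15/50 v 30/100. Power at two-sided 0.05 is about 40% for deaths of 10% v 20%, 67% for SAEs of 30% v 50%, and 73% for SAEs of 20% v 40% (all rates assumed). No additional patients are required.
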